11 MEASUREMENT OF EFFECT

11.1 Antitumor Effect – Solid Tumors

For the purposes of this study, participants should be re-evaluated for response every 8 weeks.

In addition to a baseline scan, confirmatory scans should also be obtained 8 weeks following initial documentation of objective response.

Response will be evaluated during surgical resection and on histopathology. Major pathologic response will be defined as less than 5% viable tumor cells left in the pancreatic resection specimen.

Progression will be evaluated in this study using the new international criteria proposed by the Response Evaluation Criteria in Solid Tumors (RECIST) guideline (version 1.1) [*Eur J Ca* 45:228-247, 2009]. Changes in the largest diameter (unidimensional measurement) of the tumor lesions and the shortest diameter in the case of malignant lymph nodes are used in the RECIST criteria.

11.1.1 Definitions

Evaluable for Target Disease response. Only those participants who have measurable disease present at baseline, have received at least one cycle of therapy, and have had their disease re-evaluated will be considered evaluable for target disease response. These participants will have their response classified according to the definitions stated below. (Note: Participants who exhibit objective disease progression prior to the end of cycle 1 will also be considered evaluable.)

Evaluable Non-Target Disease Response. Participants who have lesions present at baseline that are evaluable but do not meet the definitions of measurable disease, have received at least one cycle of therapy, and have had their disease re-evaluated will be

considered evaluable for non-target disease. The response assessment is based on the presence, absence, or unequivocal progression of the lesions.

11.1.2 Disease Parameters

Measurable disease. Measurable lesions are defined as those that can be accurately measured in at least one dimension (longest diameter to be recorded) as ≥ 20 mm by chest x-ray or ≥ 10 mm with CT scan, MRI, or calipers by clinical exam. All tumor measurements must be recorded in millimeters (or decimal fractions of centimeters).

Note: Tumor lesions that are situated in a previously irradiated area might or might not be considered measurable.

Malignant lymph nodes. To be considered pathologically enlarged and measurable, a lymph node must be ≥ 15 mm in short axis when assessed by CT scan (CT scan slice thickness recommended to be no greater than 5 mm). At baseline and in follow-up, only the short axis will be measured and followed.

Non-measurable disease. All other lesions (or sites of disease), including small lesions (longest diameter <10 mm or pathological lymph nodes with ≥ 10 to <15 mm short axis), are considered non-measurable disease. Bone lesions, leptomeningeal disease, ascites, pleural/pericardial effusions, lymphangitis cutis/pulmonitis, inflammatory breast disease, abdominal masses (not followed by CT or MRI), and cystic lesions are all considered non-measurable.

Note: Cystic lesions that meet the criteria for radiographically defined simple cysts should not be considered as malignant lesions (neither measurable nor non-measurable) since they are, by definition, simple cysts.

‘Cystic lesions’ thought to represent cystic metastases can be considered as measurable lesions, if they meet the definition of measurability described above. However, if non-

cystic lesions are present in the same participant, these are preferred for selection as target lesions.

Target lesions. All measurable lesions up to a maximum of 2 lesions per organ and 5 lesions in total, representative of all involved organs, should be identified as **target lesions** and recorded and measured at baseline. Target lesions should be selected on the basis of their size (lesions with the longest diameter), be representative of all involved organs, but in addition should be those that lend themselves to reproducible repeated measurements. It may be the case that, on occasion, the largest lesion does not lend itself to reproducible measurement in which circumstance the next largest lesion which can be measured reproducibly should be selected. A sum of the diameters (longest for non-nodal lesions, short axis for nodal lesions) for all target lesions will be calculated and reported as the baseline sum diameters. If lymph nodes are to be included in the sum, then only the short axis is added into the sum. The baseline sum diameters will be used as reference to further characterize any objective tumor regression in the measurable dimension of the disease.

Non-target lesions. All other lesions (or sites of disease) including any measurable lesions over and above the 5 target lesions should be identified as **non-target lesions** and should also be recorded at baseline. Measurements of these lesions are not required, but the presence, absence, or in rare cases unequivocal progression of each should be noted throughout follow up.

11.1.3 Methods for Evaluation of Disease

All measurements should be taken and recorded in metric notation using a ruler, calipers, or a digital measurement tool. All baseline evaluations should be performed as closely as possible to the beginning of treatment and never more than 4 weeks before the beginning of the treatment.

The same method of assessment and the same technique should be used to characterize

each identified and reported lesion at baseline and during follow-up. Imaging-based evaluation is preferred to evaluation by clinical examination unless the lesion(s) being followed cannot be imaged but are assessable by clinical exam.

Conventional CT and MRI. This guideline has defined measurability of lesions on CT scan based on the assumption that CT thickness is 5mm or less. If CT scans have slice thickness greater than 5 mm, the minimum size of a measurable lesion should be twice the slice thickness. MRI is also acceptable in certain situations (e.g. for body scans).

Use of MRI remains a complex issue. MRI has excellent contrast, spatial, and temporal resolution; however, there are many image acquisition variables involved in MRI, which greatly impact image quality, lesion conspicuity, and measurement. Furthermore, the availability of MRI is variable globally. As with CT, if an MRI is performed, the technical specifications of the scanning sequences used should be optimized for the evaluation of the type and site of disease. Furthermore, as with CT, the modality used at follow-up should be the same as was used at baseline and the lesions should be measured/assessed on the same pulse sequence. It is beyond the scope of the RECIST guidelines to prescribe specific MRI pulse sequence parameters for all scanners, body parts, and diseases. Ideally, the same type of scanner should be used and the image acquisition protocol should be followed as closely as possible to prior scans. Body scans should be performed with breath-hold scanning techniques, if possible.

FDG-PET. While FDG-PET response assessments need additional study, it is sometimes reasonable to incorporate the use of FDG-PET scanning to complement CT scanning in assessment of progression (particularly possible 'new' disease). New lesions on the basis of FDG-PET imaging can be identified according to the following algorithm:

- (a) Negative FDG-PET at baseline, with a positive FDG-PET at follow-up is a sign of PD based on a new lesion.
- (b) No FDG-PET at baseline and a positive FDG-PET at follow-up: If the positive FDG-PET at follow-up corresponds to a new site of disease confirmed by CT, this is PD. If the positive FDG-PET at follow-up is not confirmed as a new site of disease

on CT, additional follow-up CT scans are needed to determine if there is truly progression occurring at that site (if so, the date of PD will be the date of the initial abnormal FDG-PET scan). If the positive FDG-PET at follow-up corresponds to a pre-existing site of disease on CT that is not progressing on the basis of the anatomic images, this is not PD.

(c) FDG-PET may be used to upgrade a response to a CR in a manner similar to a biopsy in cases where a residual radiographic abnormality is thought to represent fibrosis or scarring. The use of FDG-PET in this circumstance should be prospectively described in the protocol and supported by disease-specific medical literature for the indication. However, it must be acknowledged that both approaches may lead to false positive CR due to limitations of FDG-PET and biopsy resolution/sensitivity.

Note: A ‘positive’ FDG-PET scan lesion means one which is FDG avid with an uptake greater than twice that of the surrounding tissue on the attenuation corrected image.

PET-CT. At present, the low dose or attenuation correction CT portion of a combined PET-CT is not always of optimal diagnostic CT quality for use with RECIST measurements. However, if the site can document that the CT performed as part of a PET-CT is of identical diagnostic quality to a diagnostic CT (with IV and oral contrast), then the CT portion of the PET-CT can be used for RECIST measurements and can be used interchangeably with conventional CT in accurately measuring cancer lesions over time. Note, however, that the PET portion of the CT introduces additional data which may bias an investigator if it is not routinely or serially performed.

MIBG (meta-iodobenzylguanidine). The following is recommended, to assure high quality images are obtained.

Patient preparation: Iodides, usually SSKI (saturated solution of potassium iodide), are administered to reduce thyroidal accumulation of free radioiodine, preferably beginning the day prior to injection and continuing for 3 additional days (4 days

total). For infants and children, one drop t.i.d. is sufficient, for adolescents 2 drops t.i.d., and for adults 3 drops t.i.d. Participants and/or parents are asked about exposure to potential interfering agents. If none is noted, an indwelling intravenous line is established. The dose of MIBG is administered by slow intravenous injection over 90 seconds.

Images from the head to the distal lower extremities should be obtained.

I-123MIBG scintigraphy is performed to obtain both planar and tomographic images.

Planar: Anterior and posterior views from the top of the head to the proximal lower extremities are obtained for 10 minutes at 24 hours and occasionally at 48 hours following injection of 10 mCi/1.7 square meters of body surface area ($\sim 150 \mu\text{Ci/kg}$, maximum 10 mCi). Anterior views of the distal lower extremities are adequate. A large field of view dual head gamma camera with low energy collimators is preferred.

SPECT: Most participants receiving I-123 MIBG also undergo SPECT at 24 hours, using a single or multi-headed camera with a low energy collimator. The camera is rotated through 360 degrees, 120 projections at 25 seconds per stop. Data are reconstructed using filtered back projections with a Butterworth filter and a cut off frequency of 0.2-0.5. SPECT/CT may be performed at institutions with this capacity.

Ultrasound. Ultrasound is not useful in assessment of lesion size and should not be used as a method of measurement. Ultrasound examinations cannot be reproduced in their entirety for independent review at a later date and, because they are operator dependent, it cannot be guaranteed that the same technique and measurements will be taken from one assessment to the next. If new lesions are identified by ultrasound in the course of the study, confirmation by CT or MRI is advised. If there is concern about radiation exposure from CT, MRI may be used instead of CT in selected instances.

Endoscopy, Laparoscopy. The utilization of these techniques for objective tumor

evaluation is not advised. However, such techniques may be useful to confirm complete pathological response when biopsies are obtained or to determine relapse in trials where recurrence following complete response (CR) or surgical resection is an endpoint.

Tumor markers. Tumor markers alone cannot be used to assess response. If markers are initially above the upper normal limit, they must normalize for a participant to be considered in complete clinical response. Specific guidelines for both CA-125 response (in recurrent ovarian cancer) and PSA response (in recurrent prostate cancer) have been published [*JNCI* 96:487-488, 2004; *J Clin Oncol* 17, 3461-3467, 1999; *J Clin Oncol* 26:1148-1159, 2008]. In addition, the Gynecologic Cancer Intergroup has developed CA-125 progression criteria which are to be integrated with objective tumor assessment for use in first-line trials in ovarian cancer [*JNCI* 92:1534-1535, 2000].

Cytology, Histology. These techniques can be used to differentiate between partial responses (PR) and complete responses (CR) in rare cases (e.g., residual lesions in tumor types, such as germ cell tumors, where known residual benign tumors can remain).

The cytological confirmation of the neoplastic origin of any effusion that appears or worsens during treatment when the measurable tumor has met criteria for response or stable disease is mandatory to differentiate between response or stable disease (an effusion may be a side effect of the treatment) and progressive disease.

11.1.4 Response Criteria

11.1.4.1 Evaluation of Target Lesions

Complete Response (CR): Disappearance of all target lesions. Any pathological lymph nodes (whether target or non-target) must have reduction in short axis to <10 mm.

Partial Response (PR): At least a 30% decrease in the sum of the diameters of target

lesions, taking as reference the baseline sum diameters.

Progressive Disease (PD): At least a 20% increase in the sum of the diameters of target lesions, taking as reference the smallest sum on study (this includes the baseline sum if that is the smallest on study). In addition to the relative increase of 20%, the sum must also demonstrate an absolute increase of at least 5 mm. (Note: the appearance of one or more new lesions is also considered progressions).

Stable Disease (SD): Neither sufficient shrinkage to qualify for PR nor sufficient increase to qualify for PD, taking as reference the smallest sum diameters while on study.

11.1.4.2 Evaluation of Non-Target Lesions

Complete Response (CR): Disappearance of all non-target lesions and normalization of tumor marker level. All lymph nodes must be non-pathological in size (<10 mm short axis).

Note: If tumor markers are initially above the upper normal limit, they must normalize for a patient to be considered in complete clinical response.

Non-CR/Non-PD: Persistence of one or more non-target lesion(s) and/or maintenance of tumor marker level above the normal limits.

Progressive Disease (PD): Appearance of one or more new lesions and/or *unequivocal progression* of existing non-target lesions. *Unequivocal progression* should not normally trump target lesion status. It must be representative of overall disease status change, not a single lesion increase.

Although a clear progression of “non-target” lesions only is exceptional, the opinion of the treating physician should prevail in such circumstances, and the progression

status should be confirmed at a later time by the review panel (or Principal Investigator).

11.1.4.3 Evaluation of New Lesions

The finding of a new lesion should be unequivocal (i.e. not due to difference in scanning technique, imaging modality, or findings thought to represent something other than tumor (for example, some ‘new’ bone lesions may be simply healing or flare of pre-existing lesions). However, a lesion identified on a follow-up scan in an anatomical location that was not scanned at baseline is considered new and will indicate PD. If a new lesion is equivocal (because of small size etc.), follow-up evaluation will clarify if it truly represents new disease and if PD is confirmed, progression should be declared using the date of the initial scan on which the lesion was discovered.

11.1.4.4 Evaluation of Best Overall Response

The best overall response is the best response recorded from the start of the treatment until disease progression/recurrence (taking as reference for progressive disease the smallest measurements recorded since the treatment started). The patient's best response assignment will depend on the achievement of both measurement and confirmation criteria.

For Participants with Measurable Disease (i.e., Target Disease)

Target Lesions	Non-Target Lesions	New Lesions	Overall Response	Best Overall Response when Confirmation is Required*
CR	CR	No	CR	≥ 4 wks Confirmation**
CR	Non-CR/Non-PD	No	PR	≥ 4 wks Confirmation**

CR	Not evaluated	No	PR	
PR	Non-CR/Non-PD/not evaluated	No	PR	
SD	Non-CR/Non-PD/not evaluated	No	SD	Documented at least once ≥ 4 wks from baseline**
PD	Any	Yes or No	PD	
Any	PD***	Yes or No	PD	no prior SD, PR or CR
Any	Any	Yes	PD	

* See RECIST 1.1 manuscript for further details on what is evidence of a new lesion.
 ** Only for non-randomized trials with response as primary endpoint.
 *** In exceptional circumstances, unequivocal progression in non-target lesions may be accepted as disease progression.

Note: Participants with a global deterioration of health status requiring discontinuation of treatment without objective evidence of disease progression at that time should be reported as “*symptomatic deterioration*.” Every effort should be made to document the objective progression even after discontinuation of treatment.

For Participants with Non-Measurable Disease (*i.e.*, Non-Target Disease)

Non-Target Lesions	New Lesions	Overall Response
CR	No	CR
Non-CR/non-PD	No	Non-CR/non-PD*
Not all evaluated	No	not evaluated
Unequivocal PD	Yes or No	PD
Any	Yes	PD

* ‘Non-CR/non-PD’ is preferred over ‘stable disease’ for non-target disease since SD is increasingly used as an endpoint for assessment of efficacy in some trials so to assign

this category when no lesions can be measured is not advised

11.1.5 Duration of Response

Duration of overall response: The duration of overall response is measured from the time measurement criteria are met for CR or PR (whichever is first recorded) until the first date that recurrent or progressive disease is objectively documented (taking as reference for progressive disease the smallest measurements recorded since the treatment started, or death due to any cause. Participants without events reported are censored at the last disease evaluation).

Duration of overall complete response: The duration of overall CR is measured from the time measurement criteria are first met for CR until the first date that progressive disease is objectively documented, or death due to any cause. Participants without events reported are censored at the last disease evaluation.

Duration of stable disease: Stable disease is measured from the start of the treatment until the criteria for progression are met, taking as reference the smallest measurements recorded since the treatment started, including the baseline measurements.

11.1.6 Progression-Free Survival

Overall Survival: Overall Survival (OS) is defined as the time from randomization (or registration) to death due to any cause, or censored at date last known alive.

Progression-Free Survival: Progression-Free Survival (PFS) is defined as the time from randomization (or registration) to the earlier of progression or death due to any cause. Participants alive without disease progression are censored at date of last disease evaluation.

Time to Progression: Time to Progression (TTP) is defined as the time from randomization (or registration) to progression, or censored at date of last disease evaluation for those without progression reported.

11.1.7 Response Review

Not applicable

11.2 Antitumor Effect – Hematologic Tumors

Not applicable

11.3 Other Response Parameters

Not applicable

12 DATA REPORTING / REGULATORY REQUIREMENTS

Adverse event lists, guidelines, and instructions for AE reporting can be found in Section 7.0 (Adverse Events: List and Reporting Requirements).

12.1 Data Reporting

12.1.1 Method

The DF/HCC Office of Data Quality (ODQ) will collect, manage, and perform quality checks on the data for this study.

12.1.2 Responsibility for Data Submission

Investigative sites are responsible for submitting data and/or data forms to the Office of Data Quality (ODQ) in accordance with DF/HCC policies.

12.2 Data Safety Monitoring

The DF/HCC Data and Safety Monitoring Board (DSMB) will review and monitor study progress, toxicity, safety and other data from this study. The Board is chaired by a medical oncologist from outside of DF/HCC and its membership composed of internal and external institutional representation. Information that raises any questions about participant safety or protocol performance will be addressed by the Sponsor-Investigator, statistician and study team. Should any major concerns arise, the DSMB will offer recommendations regarding whether or not to suspend the study.

The DSMB will meet twice a year to review accrual, toxicity, response and reporting information. Information to be provided to the DSMB may include: participant accrual; treatment regimen information; all adverse events and serious adverse events reported across all sites by category; summary of any deaths on study; audit results; and a summary provided by the study team. Other information (e.g. scans, laboratory values) will be provided upon request.

12.3 Multi-Center Guidelines

This protocol will adhere to DF/HCC Policy MULTI-100 and the requirements of the DF/HCC Multi-Center Data and Safety Monitoring Plan. The specific responsibilities of the Sponsor-Investigator, Coordinating Center, and Participating Institutions and the procedures for auditing are presented in Appendix B.

13 STATISTICAL CONSIDERATIONS

13.1 Study Design/Endpoints

The primary endpoint is the rate of major pathological response (MPR) defined as <5% residual tumor cells visible in the pancreatic resection specimen. The major pathological response rate will be analyzed among all patients who start protocol therapy, including those not resected due to early progression, death or off study.

Major pathologic response (MPR) is based on the CAP grading system for response to neoadjuvant therapy in pancreatic adenocarcinoma (69) and includes both grade 0 (pathologic complete response) and grade 1 (single or small groups of cells) responses. MPR is defined specifically as <5% residual cells (70) and is attempted to allow easier cross comparison between studies by using an objective number as opposed to subjective assessment of the amount of residual cells remaining in the tumor. MPR has been correlated with outcomes and is strongly associated with improved long term outcomes in patients with resected pancreatic adenocarcinoma(70, 71).

Eligible patients with newly diagnosed resectable or borderline resectable pancreatic adenocarcinoma will be randomly assigned in a 2:1 allocation ratio to one of the two interventions: NIS793 and FOLFIRINOX chemotherapy for 8 cycles (Arm A, Experimental arm) followed by surgery, or FOLFIRINOX for 8 cycles (Arm B, Control arm) followed by surgery. The experimental (Arm A) and control arms (Arm B) will accrue 30 and 15 patients respectively. The first five patients randomized to NIS793 (Arm A) will be part of a safety lead-in. Study will pause until the last patient accrued for safety lead-in has completed two full treatment cycles (i.e., 28 days). Participants must have received at least 75% of their assigned doses of FOLFIRINOX and NIS793 to be considered evaluable for this safety analysis, unless dosing was held or reduced due to toxicity. If one or more of the first five participants enrolled does not meet this parameter for a reason other than toxicity (e.g. rapid disease progression and subsequent removal), Arm A will continue to accrue as many participants as needed to have five evaluable participants for safety assessment. Patients with borderline resectable pancreatic adenocarcinoma will receive chemoradiation after completion of systemic chemotherapy prior to surgery. As per the standard of care, the time interval between completion of neoadjuvant chemotherapy and radiation will be 2-4 weeks for patients with borderline resectable pancreatic adenocarcinoma and the interval between completion of neoadjuvant treatment and surgery for all patients will be between 2-8 weeks.

We will compare experimental arm to the control arm to see if it has improved the major pathological response rate (MPR). The experimental treatment will be claimed to be successful if

$\Pr(p.e > p.c + 0.05 | \text{data}) > \theta_t$, where $p.e$ and $p.c$ are the MPR for the experimental arm and control arm, respectively, and θ_t is the threshold value. We assume the prior distributions $p.e \sim \text{Beta}(0.3, 0.7)$ and $p.c \sim \text{Beta}(0.13, 0.87)$, which reflect that the expected MPR being 30% in experimental arm and 13% in control arm.

We set the threshold, $\theta_t = 0.74$, so that the type I error is controlled to be less than 20%. That is, if the experimental arm has the same MPR as the control arm with response rate of 0.13, the probability of claiming its success is less than or equal to 20%. The results are presented in Table 1. In this setting, we have 67.7% power to claim the success of an experimental arm with MPR being 30%. That is, when MPR being 30% in the experimental arm, the probability of claiming its success is 67.7%. Table 1 shows the operating characteristics for the design.

Table 1. Operating characteristics for MPR being 0.13 in control arm and MPR varying from 0.08 to 0.40 in experiment arm. The maximum sample size for experimental and control arms are N=30 and 15, respectively.

MPR in experimental arm	Percentage of claiming success
0.08	0.064
0.13	0.162
0.26	0.563
0.30	0.677
0.35	0.795
0.40	0.884

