13.5 Analysis of Primary Endpoints

Patients' demographic and clinical characteristics will be summarized using descriptive statistics. Specifically, categorical covariates will be summarized by frequencies and percentages and their associations between groups will be assessed using the Chi Square test or Fisher's exact test. Continuous covariates will be summarized by means, standard deviations, medians and ranges, and the difference between groups will be assessed using the t-test or Wilcoxon rank sum test.

We will estimate the MPR for each arm. Due to the small sample size, we will estimate the MPR with its 95% exact confidence interval (CI). Among 30 patients treated in experimental arm, assuming 9 out of 30 patients have achieved primary endpoint, the 95% CI of MPR will be (0.15, 0.49). Additionally, generalized linear regression models will be explored to evaluate the

associations between the endpoint of MPR and covariates of interest.

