13.7.2 Evaluation of the Primary Efficacy Endpoint

Major pathologic response will be analyzed according to modified intent-to-treat, excluding patients determined to be ineligible at randomization or who withdraw consent prior to starting any protocol therapy.

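### Does the success rule need a minimum Arm A response rate, because 3/30 v 0/15 already counts as success?

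*Combined protocol and SAP*

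**What the plan says.** Section 13.1 defines the primary comparison: "The experimental treatment will be claimed to be successful if" Pr(p.e > p.c + 0.05 | data) is greater than 0.74, where p.e and p.c are the MPR in Arms A and B. The priors are Beta(0.3, 0.7) for Arm A and Beta(0.13, 0.87) for Arm B, "which reflect that the expected MPR being 30% in experimental arm and 13% in control arm". The arms have 30 and 15 patients.

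The type I error limit of 20% is stated for one situation: "if the experimental arm has the same MPR as the control arm with response rate of 0.13". Table 1 gives a 0.162 probability of success in that case and 0.677 when Arm A has 30%.

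The denominator is everyone who starts protocol therapy, "including those not resected due to early progression, death or off study". Section 13.7.2 adds: "Major pathologic response will be analyzed according to modified intent-to-treat". Section 13.5 reports each arm's MPR with an exact 95% interval. Section 13.4 plans no interim efficacy analysis, so the rule is applied once. None of these sections sets a minimum Arm A rate or lists the response counts that qualify as success.

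**The concern.** With no responders among 15 controls, the control posterior is Beta(0.13, 15.87). Its median is 0.02%, and 95% of its mass lies below 5%. Three responders in Arm A are then enough. This is the only successful outcome with an observed Arm A rate below 13%. With 0 to 4 control responders it is also the only place where an observed 10-point difference passes; elsewhere in that range the boundary needs 13.3 points.

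After 3/30 the plan's own prior and data put the probability that Arm A's true MPR exceeds 13% at only 29%. The trial could therefore be called positive for an arm that probably responds less often than the plan expected from chemotherapy alone. A floor of 4/30 seems to prevent this almost without cost, since power at 30% v 13% falls by only 0.1 point.

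**Working it through.** **Inputs.** From 13.1: margin 0.05, threshold 0.74, the two priors, 30 and 15 patients, assumed MPR 30% and 13%. I assume exactly 30 and 15 are analysed.

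**Step 1: reproduce Table 1.** With x responders in Arm A and y in Arm B, the posteriors are Beta(0.3 + x, 30.7 − x) and Beta(0.13 + y, 15.87 − y). Mark each of the 31 × 16 = 496 outcomes as success if the posterior probability exceeds 0.74, then sum Binomial(30, p.e) × Binomial(15, p.c) over the successes, with p.c = 0.13.

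| Arm A MPR | Table 1 | Exact | Exact with 4/30 floor |
|---|---|---|---|
| 0.08 | 0.064 | 0.063 | 0.035 |
| 0.13 | 0.162 | 0.157 | 0.132 |
| 0.26 | 0.563 | 0.559 | 0.556 |
| 0.30 | 0.677 | 0.680 | 0.679 |
| 0.35 | 0.795 | 0.801 | 0.801 |
| 0.40 | 0.884 | 0.885 | 0.885 |

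Table 1 is reproduced to within 0.6 point, which would fit simulation error if the table was simulated. The 20% limit is met without a floor. It is also met at a common 10% (14.8%) and a common 8% (13.6%).

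**Step 2: the weight of the disputed outcome.** At 13% in both arms its probability is C(30,3) × 0.13³ × 0.87²⁷ × 0.87¹⁵ = 0.2077 × 0.1238 = 0.0257. This is part of the 0.157 above, so the plan's error rate already includes it.

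**Step 3: is it weaker evidence than the other boundary outcomes?**

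| Control responders | Fewest Arm A responders for success | Posterior | One-sided Fisher p |
|---|---|---|---|
| 0 | 3 | 0.807 | 0.286 |
| 1 | 6 | 0.826 | 0.241 |
| 2 | 8 | 0.784 | 0.269 |
| 3 | 10 | 0.761 | 0.285 |
| 4 | 12 | 0.747 | 0.294 |

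Its posterior is above three of the other four, and its Fisher p, which uses no prior, lies within their range. With 2/30 v 0/15 the posterior is 0.585, so the boundary cannot be placed more finely at zero control responders.

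Equal observed differences are not equal evidence. For 3/30 v 0/15, Fisher p = C(30,3)/C(45,3) = 4,060/14,190 = 0.286. For 5/30 v 1/15, also a 10-point difference, p = [15 × C(30,5) + C(30,6)]/C(45,6) = (2,137,590 + 593,775)/8,145,060 = 0.335. The second is weaker, and the rule rejects it (posterior 0.735).

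**Step 4: what the rule asks.** After 3/30 v 0/15 the posterior means are 3.3/31 = 10.6% and 0.13/16 = 0.8%, a difference of 9.8 points against a margin of 5. Whether Arm A exceeds 13% is a different question. If control MPR really were 13%, 0/15 would occur with probability 0.87¹⁵ = 12.4%, so 0/15 is itself evidence of a lower control rate.

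**Step 5: the price of a floor.** A 4/30 floor removes only 3/30 v 0/15. The power lost is C(30,3) × p.e³ × (1 − p.e)²⁷ × (1 − p.c)¹⁵. At 30% v 13% this is 0.0009. At 2% v 12% it is 0.2224 × 0.7386 = 0.164. The low control rates below are assumptions; every true difference exceeds 5 points.

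| Control v Arm A | Power, plan's rule | Power with floor |
|---|---|---|
| 13% v 30% | 68.0% | 67.9% |
| 5% v 22% | 74.6% | 72.2% |
| 5% v 15% | 50.9% | 43.0% |
| 3% v 13% | 54.3% | 41.1% |
| 2% v 15% | 69.5% | 56.9% |
| 2% v 12% | 56.1% | 39.7% |

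**The case for a change.** The best case for a floor is that it gives real protection and is cheap at the design values. False success falls from 14.8% to 10.0% at a common 10%, and from 13.6% to 7.3% at a common 8%. In the 0.08 row of Table 1, where Arm A is worse than control, this single outcome supplies 0.0271 of 0.0625, or 43% of the false claims. The control prior also helps the outcome to pass. The intervals in 13.5 (2% to 27% for 3/30) would show the uncertainty but not alter the declared result.

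Those figures stand. They show that a stricter rule errs less often, which is true of any stricter rule. All the starting values are below the plan's 20% limit. The floor would also still accept 4/30 v 0/15, where the probability that Arm A exceeds 13% is only 51%, so it barely answers the worry behind it.

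A second argument is that modified intent-to-treat exclusions change the denominators: with 27 and 13 analysed (an assumption), false success at 13% is 20.6%, and a 13% floor brings it to 16.8%. This too is correct, but it concerns how the 0.74 threshold is calibrated at other sample sizes. Section 13.2 aims for 45 patients who receive therapy, so withdrawals before treatment should not reduce that number.

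It is also fair that a reader cannot see from 13.1 that 3/30 v 0/15 passes. Listing the boundary would make this visible but would change no result.

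**Conclusion.** The concern does not hold. The rule does what 13.1 says, Table 1 is reproduced, and the stated limit is met with 3/30 v 0/15 included (15.7% exact, against at most 20%). That outcome is as strong, comparatively, as the other boundary outcomes. It looks odd only when Arm A is set against the planning value of 13% instead of the randomised control.

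A 13% floor would gain 2.6 points of type I error at the design null. Its power cost runs from 0.1 point at 30% v 13% to 16.4 points at 2% v 12%. The documents do not rule out low control rates, because unresected patients stay in the denominator. Reasonable statisticians could choose either way, so the absence of a floor is a design preference. The figures assume 30 and 15 analysed patients and a single final analysis.
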